At the end of the pilot study, emigration was the most important cause of dropout. Subjects with plans of migration in the following months during the study will be excluded. To avoid contamination risk, if a family member is selected, only one member per family will be included.

Sampling: Community members will be invited to a medical screening at the CHC. Those with high risk will be identified using the Latin America Finish Diabetes Risk Score (LA-FINRISC). The LA-FINRISC is a non-invasive tool that includes age, body mass index (BMI), waist circumference, physical activity, daily consumption of fruits and vegetables, history of hyperglycemia, history of antihypertensive drug treatment, and family history of diabetes, assigning a score ranging from 0 to 26 points. In Venezuelan adults, 9 points are the best score (sensitivity 71.4% + specificity 65.4%) to detect subjects with impaired glucose tolerance²⁵. Those with an LA-FINRISC \geq 10 points and having the inclusion criteria will be invited to laboratory test and medical evaluation and those with laboratory criteria will be invited to participate.

Sample Size: The formula to compare two mean was used. Based on preliminary results of our pilot study, the aim was to detect a two-fold reduction of weight loss in the intensive group (mean = 5.0 kg, standard deviation = 4.9) compared with only DPP (mean = 2.4 kg, standard deviation = 1.9). Using a Beta error of 0.2 and an Alpha error of 0.01, the sample size required for each group is 50, and assuming a 20% of loss to follow up (based on the pilot study), and a 30% additional to ensure representativeness of the sample and power, the sample size will be incremented to **78** participants in each group, total sample size of 156 participants.

Randomization: Eligible participants will be randomly assigned to hybridized LSI or standard care with 1:1 allocation.

Implementation:

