More details of the implementation process results are in the Supplements (Table 2). Reasons of dropout were: emigration 3 (42.9%), family problems 2 (28.6%), financial problems 1 (14.3%), did not answer 1 (14.3%). Although this pilot study was implemented in the context of a complex humanitarian emergency in Venezuela, with a severe failure of basic services including extensive and repetitive blackouts, scare of gas and gasoline, and the highest inflation rate in the world³², without a budget to provide proper tools to the participants and implementers, the intervention is feasible with a 26.9% of dropout, which is expected in community base scenarios, and with high average of attendance (72.1% - Fidelity). Participants considered the intervention acceptable and appropriate. The mean of weight loss was 2.45 kg in three months and 31.6% had reached the third-month goal.

A second concern was to assess the acceptance of a LELD intervention in Venezuelans. A pilot study to assess its implementation was undertaken in adults with increased weight. A nutritionist provided weekly group sessions recommending “Home-Made” LEDL replacing usual foods during a month, reintroduction diet for 1 week, and then four weekly educative sessions of maintenance weight program. 14 participants assisted to the

first session and nine started the program. In four weeks of intervention, the average weight reduction was 3.23 kg. Using a Likert scale, participants implementing the program (n=9) reported: frequency of secondary symptoms (dizziness, gastrointestinal disorders, headache, hunger, etc.) 0.8/3 points (never = 0 and very frequent = 3); severity of secondary symptoms: 0.5/3 points (mild = 0 and severe = 3); acceptability (satisfaction): 4.9/5 (totally disagree = 1 and totally agree = 5); appropriateness = 5/5 (totally disagree = 1 and totally agree = 5). In summary, the participants reported the intervention acceptable, appropriate, effective, and with a low frequency and intensity of secondary symptoms.

Effectiveness – Intervention. The Flowchart is presented in Supplements (Figure 3).

Duration: 6 months. The DPP has two phases, weight reduction to reach 7% of weight loss during the first six months, and weight maintenance during the next six months. This project aims to evaluate a new strategy to improve the effectiveness of weight reduction in the initial semester.

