Aims comparing effectiveness: I will be done using an intention-to-treat analysis. To evaluate the distribution of values at baseline and after follow-up, Student t-test will be used to compare weight at baseline and at the end of the intervention, as well as, other continues variables (blood pressure, lipid profile, blood glucose, physical activity level, etc.). Chi-square test will be applied to assess the different proportion of subjects that reached their weight goal. To assess the implementation process will be applied the Implementation Outcomes Framework, this was partially reported in this project (Table 1), additionally, it will be evaluated the cost of the intervention. Implementation outcomes will be presented as proportions, means, and qualitative comments.

Research team and their role:

Two Lown Scholars, PI, and mentor designed the study, are going to supervise the implementation, do the analysis, and write the paper. An investigator from Icahn School of Medicine at Mount Sinai, New York, NY, USA, four co-investigators from the EVESCAM Research team, collaborated with the design and will collaborate with supervision of implementation, data analysis, and critical review. Implementers will coordinate intervention. The organizational structure includes: (a) Collaborative coordinating institution: Venezuelan Society of Internal Medicine (SVMI), Caracas, Venezuela; (b) Cardiometabolic Unit, Barquisimeto, Venezuela, where it is located laboratory (c) Field center: the Community health care center (d) Investigators (e) International consultants; (f) Local coordinators (n=2); (g) Nutritionist and research assistant (n=2); (h) Certified Coach (n=1). The budget will be administrated by the Foundation for Clinical, Public Health, and Epidemiological Research of Venezuela (FISPEVEN). See support letters

Timeline:

Months	1 - 3	4 - 9	10 – 12
Screening and Medical Evaluation	X		
Intervention		X	
Data analysis and draft writing			X

Challenges and Alternative Response

According to the observed in the pilot studies, there are two major challenges: a) *high dropout and lower fidelity*: a 20% of dropout is expected, however, implementers will be trained to be in continuous contact with the participants and maintain them highly motivated. Workshops of cooking and group physical activities are two

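### The fixed t-test on weight does not match a trial sized on weight loss; the primary analysis should compare month-6 weight between arms, adjusted for baseline weight

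*Protocol*

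**What the plan says.** The Data analysis plan says of the effectiveness aims: "I will be done using an intention-to-treat analysis". The next sentence fixes the test for weight: "Student t-test will be used to compare weight at baseline and at the end of the intervention". The same test is to serve blood pressure, lipids, glucose and the other continuous measures. No covariate is named, and the text does not say whether the two arms or the two time points are compared. For the binary outcome, "Chi-square test will be applied to assess the different proportion of subjects that reached their weight goal"; the goal, set under the intervention descriptions, is a 7% weight loss in both arms.

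The Sample Size section is built on weight loss: mean 5.0 kg (SD 4.9) in the intensive arm and 2.4 kg (SD 1.9) under DPP alone, alpha 0.01, beta 0.2. This gives 50 per group, raised to 78 per group and 156 in total, "assuming a 20% of loss to follow up (based on the pilot study" and a further 30%. Challenges and Alternative Response repeats that "a 20% of dropout is expected". The hypothesis is that the hybrid programme doubles the weight loss of DPP alone at six months.

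**The concern.** The hypothesis and the sample size concern a difference between arms in weight change. The analysis sentence concerns weight at two time points. Two readings follow naturally from its words, and neither delivers what was sized.

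- **End weight compared between arms.** The relevant spread is that of body weight across people, which is normally much larger than the spread of weight loss over six months. A 2.6 kg difference is then hard to see.
- **Before versus after within each arm.** This asks whether each arm lost weight. It gives no estimate of the difference between arms, and a significant result in one arm but not in the other is not a test of that difference.

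Either way, the trial could miss the effect it was designed to find, or answer a different question. Baseline weight has to be known in any case, because the 7% goal is measured from it.

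The second issue is smaller. A t-test needs a month-6 weight, so delivering an intention-to-treat result depends on obtaining that weight from those who stop sessions.

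**Working it through.** **Inputs.** From Sample Size: means 5.0 and 2.4 kg, SDs 4.9 and 1.9 kg, alpha 0.01, power 0.80, 50 then 78 per group, 20% loss. Sidedness is not stated; two-sided is used because it comes close to the plan's 50 (48, against 42 one-sided). Assumed, not in the documents: body-weight SD of 10 to 18 kg in each arm at month 6.

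**1. The plan's own figure.** Difference = 5.0 − 2.4 = 2.6 kg. Sum of variances = 4.9² + 1.9² = 24.01 + 3.61 = 27.62.

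n per group = 27.62 × (2.576 + 0.842)² / 2.6² = 47.7, so 48 by normal approximation. With the t distribution, power at 50 per group is 0.81 (pooled) or 0.80 (Welch), so the stated 50 is reproduced. Then 50 × 1.2 × 1.3 = 78 per group. The sizing therefore assumes a two-group comparison of weight loss.

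**2. Power on weight loss.** At 20% loss, 78 × 0.80 = 62.4 per arm have an end weight. SE = √(27.62/62.4) = 0.665 kg; 2.6/0.665 = 3.91; power = Φ(3.91 − 2.576) = 0.91.

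**3. Power on unadjusted end weight.** SE = SD × √(2/62.4); power = Φ(2.6/SE − 2.576) + Φ(−2.6/SE − 2.576).

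| Assumed body-weight SD | SE (kg) | 2.6/SE | Power |
|---|---|---|---|
| 10 kg | 1.79 | 1.45 | 0.13 |
| 18 kg | 3.22 | 0.81 | 0.04 |

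**4. Why baseline adjustment restores the match.** Analysing change is the same as analysing end weight with the slope on baseline fixed at 1. ANCOVA estimates that slope, so apart from small-sample cost its residual variance is no larger than that of change. Power should then be at least about the 0.91 in step 2. The size of any further gain cannot be computed, because the documents give no baseline-to-end correlation.

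**5. Secondary point: missing weights.** 0.20 × 156 = 31.2, so about 31 would have no month-6 weight if everyone lost is unweighed, leaving about 125. To show the scale only, suppose those weighed lose 5.0 and 2.4 kg and those lost to follow-up lose nothing:

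- Equal 20% loss: 0.80 × 2.6 = 2.08 kg. The ratio stays at 5.0/2.4 = 2.08. With all 78 per arm, the summed variance is 0.8 × 27.62 + 0.16 × (5.0² + 2.4²) = 27.02, SE = √(27.02/78) = 0.589, and power is 0.83.
- 25% hybrid, 15% DPP: 5.0 × 0.75 − 2.4 × 0.85 = 3.75 − 2.04 = 1.71 kg, ratio 1.84.
- 15% hybrid, 25% DPP: 4.25 − 1.80 = 2.45 kg, ratio 2.36.

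The two unequal splits are assumptions, and they move the ratio in opposite directions.

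**The case against.** **The test may be meant for change.** The sizing uses weight loss, so the authors may intend a two-sample t-test on change. If so, power is about 91% and the mismatch disappears; adjustment would then be a modest refinement. This is a fair reading of intent, but the sentence does not say it. Choosing among readings after the data are in is what a fixed plan should prevent.

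**The power loss rests on an outside SD.** This stands. The 13% to 4% range depends on an assumed 10 to 18 kg and should be read as an order of magnitude.

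**A reader might infer that the protocol contradicts its own intention-to-treat promise and will compare only about 125 completers.** The documents do not support that. The promise comes immediately before the tests and governs them. A t-test can run on all 156 once a rule for missing weights is set, and the chi-square denominator is not fixed. Both are commonly left to a statistical analysis plan, which is not shown here, so their absence is not a finding.

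**A reader might also infer a biased result.** The documents establish neither size nor direction. Non-compliance with the total diet replacement, named under Challenges and Alternative Response, is not loss to follow-up: someone who abandons the diet can still be weighed. Nor does the pilot's dropout ("the intervention is feasible with a 26.9% of dropout") bound the trial's loss. It is a three-month figure from an unfinished six-month pilot of one programme, and three of its seven dropouts emigrated, whereas in the trial "Subjects with plans of migration in the following months during the study will be excluded".

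**Adjustment does not recover missing people.** Correct. ANCOVA by itself omits anyone without a month-6 weight, and a mixed model recovers little from those who leave early. Adjustment answers the first issue; only weighing people, and a stated handling of the remainder, answers the second.

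**Conclusion.** The point holds as a mismatch between the analysis fixed and the quantity sized. As worded, the t-test is either a between-arm test of end weight, with power of roughly 13% to 4% at two-sided alpha 0.01 (about 62 per arm, body-weight SD assumed 10 to 18 kg), or a within-arm test that does not compare the arms. A t-test on change would match the sizing, at about 91%, but is not what the sentence says. The change is worth making before the data are analysed; confidence is medium because the intended reading is uncertain.

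The missing-weight issue is secondary. About 31 of 156 would lack an end weight at the planned loss if all those lost are unweighed. This is a reason to secure the intention-to-treat answer, not evidence that a completer analysis is planned or that the result would be biased.

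**What to change.** **Primary analysis.** State that month-6 weight will be compared between the randomised arms, adjusted for baseline weight: ANCOVA, or a mixed model including month 3 if weight is recorded at that encounter (the variable list is in a supplement that is not shown). Report the adjusted difference in kg with its confidence interval. Apply the same form to the other continuous outcomes.

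**To support the intention-to-treat promise.**
- Seek the month-6 weight from everyone randomised, including those who stop sessions. A physician encounter at month six is already planned for all participants.
- For the 7% goal, keep the chi-square, with all randomised as the denominator and missing counted as not reached.
- Add one sensitivity analysis with missing month-6 weight set to baseline.

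**Cost.** Protocol wording, slightly more analysis work, and effort to weigh people who have stopped attending. No new scheduled visit is needed. The downside is a less favourable goal percentage: at 20% missing, 0.80 times the rate among those weighed.

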This process is based on the transcultural Diabetes Nutrition Algorithm (tDNA)²³ adapted to Venezuela²⁴, which includes a stepwise an approach to detect subjects at risk using locally validated tool (LA-FIDNRISC)²⁵, and a protocolized intervention to provide medical nutrition therapy that includes structured low-calorie meal plan, diabetes-specific meal replacements, as well as, start or increase physical activities, get enough sleep, and tobacco cessation. (Figure 2 – Supplement). Our work also includes cultural adaption of the DPP content to the Venezuelan population (e.g. change the names of foods, units of measure, incorporate local healthy foods, warning for unhealthy traditions) and the implementation of two pilot studies (More details below).

To prevent T2D effectively, LSI programs need to induce weight loss. In the DPP, weight reduction was the main predictor of a lower incidence of T2D, each kilogram lost was related with 16% lower incidence²⁶. Total diet replacement (TDR) with low-energy liquid-diet or solid diet (825–853 kcal/day) is an effective strategy to reduce weight²⁷. In the PREVIEW study, 2224 participants with prediabetes and obesity received a low energy

diet during 8-week and presented a mean weight loss of $10.7 \pm 0.4 \text{ kg}^{28}$, and 83.5% achieved the target of $\geq 8\%$ weight reduction, the three-years expected incidence of T2D was only 4%, independent on the intervention used post-weight-loss²⁹. However, effectiveness of intervention including initial rapid weight loss is ignored in primary care levels in Venezuela. In order to improve the effectiveness of T2D prevention programs are proposed the following objectives:

- To compare the weight loss achieved of two LSI programs in a community health center of Venezuela: **a)** A hybrid LSI including rapid weight loss with total diet replacement (TDR), then medical nutrition therapy (MNT), and the DPP, VS **b)** only the DPP.
- To evaluate the change of cardiometabolic risk factors between groups.
- To evaluate the implementation process.

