Our hypothesis is: after six months of intervention, subjects receiving a hybridized LSI (TDR+MNT+DPP) will double the weight loss of those that only receive DPP (This is based on the pilot study – see below). If this outcome is achieved, it will have an enormous impact in the way that the DPP should be provided in the primary health care systems in developing countries, increasing the effectiveness of weight reduction, and in consequence, improving cardiovascular health.

Approach

Design: A pragmatic mix trial was designed with two groups a) subjects receiving a hybridized LSI (TDR-MNT-DPP) and b) only DPP.

Population: In Venezuela, there are many community health care centers (CHCs) attended by general physicians. Many of these are “communal houses”, with different activities like dancing, aerobics, yoga, karate, etc. The CHC selected is in Mérida city, at the Andes region, with around 508.988 inhabitants, in 2018. The population is organized in "Communal Councils", representing a location or small sector, two or more create the "Commonwealth", representing neighborhoods or sectors. The CHC selected is in a commonwealth, mid-class urban area, easily accessible for the inhabitants. Community leaders are highly motivated to promote this kind of activities in their neighborhood.

Inclusion Criteria: Adults with 20 years or older, no personal history of T2D, $\text{BMI} \geq 25 \text{ kg/m}^2$, and high risk for T2D (see below) will be included.

Exclusion criteria: Self-report of the following conditions:

- Chronic ischemic heart disease: acute myocardial infarction, stable angina, unstable angina.
- Stroke.
- Use of anticoagulants
- Severe renal failure
- Heart failure.
- Cannot do moderate-intensity physical activity
- Cannot attend most sessions
- Pregnancy or plans of having during the next sixth months
- Cancer or chemotherapy.
- Use of medications that affect weight (e.g. levothyroxine, pregabalin, orlistat)

During the physical examination by the general practitioner:

- Peripheral obstructive arteriopathy.
- Osteoarthritis of knees, ankles or hips.
- Body mass index (BMI) $\geq 40 \text{ kg/m}^2$

- Systolic blood pressure \geq 180 mmHg or diastolic blood pressure \geq 110 mmHg.

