Low-Energy Liquid-Diet (LELD): LELD, structured food reintroduction, and then a weight-loss maintenance program have demonstrated being a feasible and acceptable strategy to lose and maintain weight during 12 months²⁷. A “home-made” milk- and fruit-juice-based diet (811 kcal/day, 64 g protein, 132 g carbohydrate, 6 g fat) will be recommended. Recipes and preparation techniques were transculturally adapted to the population using local available low-cost foods in Venezuela. A pilot study assessing acceptability, appropriateness, and feasibility of this LELD strategy in 14 Venezuelan adults with obesity is ongoing.

Implementation Process – The Pilot Studies

A major concern was the feasibility to implement an LSI program in the current environment of Venezuela. A pilot study implementing the DPP-tDNA was done in 26 adults in the CHC. Preliminary results are summarized in Table 1. Results are presented using the implementation process framework³¹.

	n	%
Feasibility		
Screening	67	100.0
Invited to Evaluation (Meet the inclusion criteria)	47	70.1
Assisted to the Evaluation (% of those invited)	36	76.6
Started the Program	26	72.2
Assisted to only 1 session	4	15.4
Drop out (total)	7	26.9
Completed 3 months of intervention (10 sessions)	19	73.1
Fidelity		
Attendance to all the sessions	5	19.2
Attended ≥ 50% sessions	18	94.7
Average of Attendance	6.6	72.1
Acceptability (Likert scale from 1 to 5 points)	4.6	92.0
Appropriateness (Likert scale from 1 to 5 points)	4.6	92.0
Effectiveness		
	n	% Goal†
Mean of weight loss (Kilograms)	2.45	88.2
Subjects that reached the weight goal of the third month	6	31.6

*The pilot study is currently ongoing; these are the results of three months of intervention (50%) with 10 sessions provided. †Goal= to lose 7% of basal weight at the six months, corresponding to 3.5% in the third month.

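### The only test stated for weight in kilograms names neither weight change nor the two arms, although the trial was designed and sized on the between-arm difference in weight loss

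*Protocol*

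**What the plan says.** The objectives at the end of the protocol's background ask "To compare the weight loss achieved of two LSI programs in a community health center of Venezuela" and, for the secondary outcomes, "To evaluate the change of cardiometabolic risk factors between groups". The hypothesis is that, after six months, "subjects receiving a hybridized LSI (TDR+MNT+DPP) will double the weight loss of those that only receive DPP".

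Under Sample Size, "The formula to compare two mean was used", with a mean loss of 5.0 kg (SD 4.9) in the intensive arm and 2.4 kg (SD 1.9) with DPP alone. The result is given as "Using a Beta error of 0.2 and an Alpha error of 0.01, the sample size required for each group is 50", later raised to 78 per arm.

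The Data analysis plan says that the effectiveness aims "will be done using an intention-to-treat analysis". It then assigns one test to weight and to the other continuous variables (blood pressure, lipids, glucose, physical activity): "Student t-test will be used to compare weight at baseline and at the end of the intervention". A chi-square test covers the proportion reaching the weight goal. No other sentence gives a test for weight in kilograms.

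**The concern.** The design asks one question: how much more weight do people lose with the hybrid programme than with DPP alone? The stated test does not answer it as worded. Its two terms are baseline and end of intervention, not hybrid and DPP, and its variable is weight, not weight lost. Two literal readings follow.

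- **Reading (i): baseline against end, within each arm.** This tests whether an arm lost weight. Both arms receive an active programme expected to cause loss, so two significant results are likely whether or not the hybrid adds anything. They could then be mistaken for evidence in its favour.
- **Reading (ii): hybrid against DPP on raw weight, at baseline and again at the end.** Randomisation makes the end comparison valid. However, each person's starting weight stays in the error term, so most of the planned power is likely to be lost.

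The chi-square test does not fill the gap. It concerns a yes/no goal and does not estimate the kilogram difference on which the sample size was set. The same wording governs the other continuous outcomes, for which the objectives ask for change between groups.

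**Working it through.** **Inputs from the protocol.** Mean losses 5.0 and 2.4 kg, so a difference d = 2.6 kg; SDs of loss 4.9 and 1.9; alpha 0.01; power 0.80; 50 per arm before inflation; 78 per arm after it; 20% expected loss to follow-up, leaving 78 × 0.8 ≈ 62. The protocol does not say whether alpha is one- or two-sided. **Assumed:** the between-person SD of body weight, which the protocol does not give, taken as 8 to 20 kg.

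**1. Reproduce the planned sample size.** The two-means formula per arm is

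n = (z₁₋α/₂ + z₁₋β)² × (SD₁² + SD₂²) / d²

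= (2.576 + 0.842)² × (24.01 + 3.61) / 6.76 = 11.68 × 27.62 / 6.76 = 47.7.

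This is close to the stated 50, and an equal-variance t-test calculation gives exactly 50. One-sided alpha gives 41.0, which does not match. The inflation also reproduces: 50 × 1.2 × 1.3 = 78. The trial was therefore sized for a two-sided, between-arm test of weight loss.

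**2. Power of that test** (Welch, noncentral t, two-sided alpha 0.01): 80% at 50 per arm, 89% at 62, 96% at 78.

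**3. Reading (i), paired t-test within an arm.** At the protocol's own means and SDs, 80% power needs only 15 people in the hybrid arm and 11 in the DPP arm, far from 50. Now let the hybrid add nothing, so that both arms lose 2.4 kg and the SDs stay at 4.9 and 1.9. For the hybrid arm at n = 50 the noncentrality is 2.4 / (4.9/√50) = 3.46.

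| n per arm | Hybrid significant | DPP significant |
|---|---|---|
| 50 | 78% | >99.9% |
| 62 | 88% | >99.9% |
| 78 | 95% | >99.9% |

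**4. Reading (ii), between-arm t-test on raw weight.** With a common SD S, n per arm = 2 × 11.68 × S² / 6.76. Power below is for d = 2.6 kg.

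| Assumed SD (kg) | n per arm for 80% power | Power at 50 | Power at 62 | Power at 78 |
|---|---|---|---|---|
| 8 | 221 | 16% | 21% | 29% |
| 10 | 346 | 10% | 13% | 17% |
| 13 | 584 | 6% | 7% | 9% |
| 16 | 885 | 4% | 5% | 6% |
| 20 | 1,382 | 3% | 3% | 4% |

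To keep 80% power, the SD could be at most 3.7 kg (50 per arm), 4.2 kg (62) or 4.7 kg (78). For scale, Table 1 reports a mean pilot loss of 2.45 kg as 88.2% of the goal, and its footnote defines the goal as "to lose 7% of basal weight at the six months, corresponding to 3.5% in the third month". If the percentage is mean loss divided by 3.5% of mean weight, mean weight was about 2.45 / 0.882 / 0.035 = 79 kg, and 4.2 to 4.7 kg is 5–6% of it. The eligibility criteria admit BMI from 25 to below 40, a 40/25 = 1.6-fold range of weight at any one height. So small an SD is not plausible.

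**5. Baseline-adjusted comparison.** A simulation (20,000 runs; change SDs 4.9 and 1.9; change assumed independent of baseline weight; baseline SD 8, 13 or 20 kg) gave power of about 80% at 50 per arm, 89–90% at 62 and 96% at 78. The planned power holds across these baseline SDs.

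**The case against.** The best defence is that the sentence is shorthand. It stands under a lead-in about comparing effectiveness, next to an intention-to-treat statement, in a 1:1 randomised trial. The chi-square sentence also omits the arms and is naturally read as comparing them. The objectives, hypothesis and sample size leave little doubt about the contrast of interest, so a reader of the whole protocol can infer a between-arm t-test on change. The opening clause about the distribution of values may even make the sentence partly descriptive. The choice between change and final value, and any baseline adjustment, could also be left to an SAP.

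Much of this stands. The intention was probably sound, and ANCOVA is a preference, not a requirement. The power figures for raw weight rest on assumed SDs, the 79 kg on one cell of a small pilot table, and the hybrid figures in step 3 on its SD staying at 4.9 when its mean loss is 2.4 kg. These affect the size of the problem, not its direction.

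The defence does not remove the mismatch. The protocol did not leave the test open: it stated one, and the words do not describe the test on which the sample size rests. Reading the arms into the sentence still leaves raw weight as the variable. Reading it as descriptive leaves the main outcome in kilograms with no test at all.

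**Conclusion.** The concern holds, and the sentence should be corrected. Of the three tests considered, only a between-arm comparison of weight loss fits 50 per arm, and the analysis text does not name it. Followed literally, the plan yields either a test that is significant in most trials even when the hybrid adds nothing, or a valid test with power between 3% and 29% over SDs of 8 to 20 kg and 50 to 78 per arm. The planned test has 80% to 96% over the same numbers per arm. The sample-size match and the DPP figures use only the protocol's inputs, with alpha read as two-sided. The hybrid before/after figures also assume an unchanged SD of 4.9, and the raw-weight powers depend on the assumed SDs. The design and the sample size are not in question.

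**What to change.** Replace the t-test sentence with wording such as: *Six-month weight (equivalently, change from baseline) will be compared between the randomised arms, adjusted for baseline weight (ANCOVA), reporting the adjusted difference with its confidence interval at the alpha of 0.01 used for the sample size.* Apply the same approach to the other continuous outcomes, since the objectives ask for their change between groups.

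The minimum that cures the mismatch is to insert *change in* and *between the randomised arms* into the existing sentence. Standard errors that allow for unequal variances are optional. Any before/after tests within an arm should be labelled descriptive.

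The cost is one sentence of protocol text. Baseline and six-month weights are already to be collected, and the sample size is unchanged.

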examples of activities that increased motivation and attendance rates. B) *Not compliance with the TDR*: In the pilot study, TDR showed being an effective way to lose weight, however, some participants didn't accept the TDR, others changed the components frequently, and some only replaced one or two main plates, to avoid these threats, well-designed recipes with lower cost available foods showed increase compliance, additionally, in the first session it will include a workshop of how to prepare different milkshakes, and how to improve its taste, and increase volume without increasing calories to avoid hunger, a large list of different milkshakes will be provided.

Ethics:

This project will be registered in ClinicalTrials.gov. This study protocol was designed in compliance with the Helsinki declaration. The protocol and informed consent forms used in this project will be reviewed and approved by an ethics committee in Venezuela before its implementation. A researcher will read all the informed consent to the participant and will explain the benefits and risk of participation in the study answering all his/her questions, this includes: rationale of the study, identification of subjects at risk, random assignment, responsibilities, duration, potential health benefits, data management (with special emphasis in their confidentiality), and willingness to participate, including that his/her participation it can last as long as the participant want (for more detail see Informed Consent). Then, if the participant decides to participate will sign the informed consent. This will take place in the primary health care center where the intervention will be done, after the campaign of screening of risk factors in the community.

Management of Secondary Effects:

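### The named Student t-test on weight fits poorly with a trial sized on weight loss with SDs of 4.9 and 1.9 kg; a baseline-adjusted robust analysis, or Welch on change, is a free improvement

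*Protocol*

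**What the plan says.** The Data analysis plan announces an intention-to-treat analysis and then states that "Student t-test will be used to compare weight at baseline and at the end of the intervention", with the same test for the other continuous variables. It does not say whether variances are pooled, and it gives no method for participants without a final weight.

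The Sample Size paragraph works with a different quantity, weight loss: "mean = 5.0 kg, standard deviation = 4.9" in the hybrid arm and "mean = 2.4 kg, standard deviation = 1.9" in the DPP-only arm. It continues: "Using a Beta error of 0.2 and an Alpha error of 0.01, the sample size required for each group is 50". The figure is then raised to 78 per arm, "assuming a 20% of loss to follow up (based on the pilot study") plus a further 30%. Allocation is 1:1, and the loss figure is not split by arm.

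Under Challenges and Alternative Response, the protocol lists dropout (20% expected) and non-compliance with the total diet replacement as two separate challenges. On the second it reports that in the pilot "some participants didn't accept the TDR".

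**The concern.** Student's test, as usually understood, assumes equal variances, while the plan's own SDs for weight loss differ by a factor of about 2.6. With equal numbers analysed this hardly matters. With unequal numbers the pooled standard error is wrong. It is too small when the arm with the larger SD has fewer completers, and too large when it has more. The type I error and the width of the confidence interval then depend on an accident of follow-up.

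The same sentence raises a second question. It names weight, whereas the hypothesis and the sample size concern weight loss. Weight varies far more between people than weight loss does, so a comparison of raw end weights would not have the power the trial was sized for.

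**Working it through.** **Inputs.** From Sample Size: mean losses of 5.0 and 2.4 kg (difference 2.6), SDs of 4.9 and 1.9, alpha 0.01, power 0.80, 50 per group raised to 78, 20% loss. From Randomization: 1:1. From the pilot results: 19 of 26 (73.1%) completed three months of the DPP, and 9 of 14 (64.3%) started the liquid diet.

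**The plan's own figure.** The average-variance SD is √((4.9² + 1.9²)/2) = √((24.01 + 3.61)/2) = 3.716. Two-sided, n = 2 × [3.716 × (2.576 + 0.842)/2.6]² = 47.7, so 48 per group. The noncentral-t version gives 50 (power 0.806). Then 50 × 1.2 × 1.3 = 78. The stated sizes are reproduced, with weight loss as the outcome and alpha 0.01 two-sided.

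**Variance ratio.** 24.01 / 3.61 = 6.65.

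**Pooled and Welch tests on weight loss.** Normal data were simulated under no difference, with SDs of 4.9 and 1.9 and at least 400,000 trials per split. The 62/62 split is 78 × 0.8. The 50/57 split applies the two pilot percentages to 78, although the first is uptake, not completion. The other splits are illustrations and do not appear in the protocol.

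| Analysed, hybrid / DPP | Pooled, nominal 1% / 5% | Welch |
|---|---|---|
| 62 / 62 | 1.1% / 5.1% | 1.0% / 5.0% |
| 50 / 57 | 1.5% / 6.4% | 1.0% / 5.0% |
| 50 / 66 | 2.1% / 7.9% | 1.0% / 5.0% |
| 66 / 50 | 0.5% / 3.1% | 1.0% / 5.0% |

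The mechanism at 50/66:
- True SE = √(24.01/50 + 3.61/66) = √0.535 = 0.73 kg.
- Pooled variance = (49 × 24.01 + 65 × 3.61)/114 = 12.38, so pooled SE = √(12.38 × (1/50 + 1/66)) = 0.66 kg, about 10% too small.
- At 66/50 the two values are 0.66 (true) and 0.73 (pooled), about 11% too large.

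**Raw end weight instead.** This needs a baseline weight SD, which the documents do not give. Assume 10 to 18 kg, with change independent of baseline.
- SD 10: arm SDs are √(100 + 24.01) = 11.14 and √(100 + 3.61) = 10.18, ratio 1.09.
- SD 18: 18.66 and 18.10, ratio 1.03.
- Even at 47 versus 70 completers, the pooled level is then only 1.0% to 1.2% (nominal 1%) and 5.1% to 5.5% (nominal 5%).
- Power at 62 per arm, alpha 0.01: with SD 10, SE = √((124.01 + 103.61)/62) = 1.92, 2.6/1.92 = 1.36, power about 11%. With SD 18, SE = 3.30, 2.6/3.30 = 0.79, power about 4%.

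**Cost of Welch.** At 50 per arm and alpha 0.01, power is 0.797 against 0.805 pooled. At 62 per arm it is 0.891 against 0.895.

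**The case against.** The case against is substantial, and most of it stands.

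- The protocol never says that variances are pooled. A statistical analysis plan, which is not shown, could specify the unequal-variance form. This stands. The point rests on the usual meaning of the test's name.
- The SDs describe weight loss, but the sentence tests weight. On end weight the distortion nearly disappears. This also stands, but it does not rescue the plan, because that test misses the quantity sized and has little power under the assumed baseline SDs.
- A reader might infer that the stated alpha is broken under the plan's own assumptions. The documents do not support that. With 1:1 allocation and one loss figure, the level is essentially nominal. It would also be so if all 78 per arm were analysed.
- A reader might infer that the hybrid arm will lose more participants because some refuse the diet, so that false positives must rise. The documents do not support that either. A participant who refuses or alters the diet can still be weighed at six months, and under intention-to-treat is still analysed. The itemised dropout reasons come from the DPP pilot: emigration, family or financial problems, and one participant who did not answer. If the DPP arm loses more, the pooled test is conservative.
- A large completion gap could also bring bias from informative missingness, which Welch's test does not cure. This is true, and it limits what the change can achieve.

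What survives is that the named test's level depends on how completion happens to fall, and that a test without this weakness costs almost nothing.

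**Conclusion.** The point holds as an improvement, not as an error in the stated alpha. For weight loss with SDs of 4.9 and 1.9 kg, the pooled test is sound at equal numbers (about 1.1% / 5.1%). It drifts in either direction when completion is unequal, from 0.5% / 3.1% at 66 hybrid versus 50 DPP to 2.1% / 7.9% at 50 versus 66. At a pilot-like 50 versus 57 the shift is modest, about 1.5% / 6.4%. These figures assume normal data, a pooled test, weight loss as the outcome and the pilot SDs.

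The mismatch between weight as tested and weight loss as sized deserves correction in the same sentence. The 4% to 11% power for end weight depends on an assumed baseline SD of 10 to 18 kg.

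The protocol gives no arm-specific SDs for blood pressure, lipids, glucose or activity, so no variance problem is shown for those outcomes.

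**What to change.** In the Data analysis plan, state that the primary comparison is the between-arm difference in six-month weight, estimated by ANCOVA adjusted for baseline weight with heteroscedasticity-robust standard errors. At minimum, specify Welch's t-test on weight change from baseline to six months.

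Either wording matches the analysis to the quantity that was sized and removes the dependence of the level on the completion split. The cost is one sentence: both weights are already collected, and no participants are added. For the Welch option the loss of power is under one percentage point (0.805 to 0.797 at 50 per arm), so the planned 78 per arm can stay.
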